### 5.2.1 SAS code for analysis

---

#### SAS code for ANCOVA analysis

ANCOVA model will contain ‘treatment’ and ‘center’ as categorical variables, and ‘baseline BCVA’ as continuous. For secondary analysis additional linear covariates might be included, such as ‘HbA1c’, ‘Blood pressure (systolic, diastolic)’, or ‘Lipid levels (cholesterol, HDL-cholesterol, LDL-cholesterol, triglycerides)’.

For the appropriate treatment difference, the treatment arms should be sorted or coded appropriately before using this model.

The ANCOVA analysis will be performed using SAS procedure PROC MIXED as below. Note that for this illustrative example:

- the data are stored in the file data\_set
- treatmentvar = treatment variable

- responsevar = dependent variable
- stratavar = stratification variable
- bsl = baseline value of the responsevar
- alpha = significance level (i.e. 0.05 produces two-sided 95% CI)
- control = control arm (Ranibizumab 0.5 mg in PRN treatment regime)

```
PROC MIXED DATA = <data_set>;
CLASS <stratavar> <treatmentvar>;
MODEL <responsevar> = <stratavar> <treatmentvar> <bsl>;
LSMEANS <treatmentvar> / PDIFF = all CL alpha = <alpha> OM;
RUN;
```

To get the one-sided p-value for the non-inferiority test (margin = 4): add -4 letters to control group and re-run the above code with alpha=0.025 and PDIFF=controlu('<control>').

To get the one-sided p-value for the superiority test (if applicable): re-run the above code with alpha=0.025 and PDIFF=controlu('<control>').

---

### SAS code for MMRM analysis

Since scheduled visit is in the repeated statement it is important to ensure that each patient has, at most, one observation per scheduled visit. This should be checked using PROC SORT and NODUPKEY.

To avoid potential problems with a bug in SAS reporting an infinite likelihood, the data will be sorted by patient and visit before using PROC MIXED.

For the appropriate treatment difference, the treatment arms should be sorted or coded appropriately before using this model.

The comparison of interest is found by using the SAS code below. Note that for this illustrative example:

- the data are stored in the file data\_set
- treatmentvar = treatment variable
- subjvar = patient identifier
- responsevar = dependent variable
- stratavar = stratification variable
- visitvar = timepoint variable
- bsl = baseline value of the responsevar
- cov = covariance structure
- alpha = significance level (i.e. 0.05 produces two-sided 95% CI)
- control = control arm (<control>)

```
PROC SORT DATA = data_set OUT = s_data_set nodupkey;
BY patient visit;
RUN;
PROC MIXED DATA = <s_data_set> METHOD=REML;
CLASS <treatmentvar> <visitvar> <subjvar>;
MODEL <responsevar> = <stratavar> <treatmentvar> <visitvar>
<treatmentvar>*<visitvar> <bsl> <visitvar>*<bsl> / SOLUTION DDFM = KR;
REPEATED <visitvar> / SUBJECT = <subjvar> TYPE = <cov> r rcorr GROUP =
<treatmentvar>;
ESTIMATE 'Average Treatment Effect'
    <treatmentvar> -1 1
    <treatmentvar>*<visitvar> -0.083 -0.083 -0.083 -0.083 -0.083
    -0.083 -0.083 -0.083 -0.083 -0.083
    -0.083 -0.083
    0.083 0.083 0.083 0.083 0.083
0.083 0.083 0.083 0.083 /cl;
RUN;
```

Using the slice option above means that the difference between treatment arms will be tested for each visit.

To get the one-sided p-value for the non-inferiority test (margin = 4): add -4 letters to control group and re-run the above code with alpha=0.025 and PDIFF=controlu('<control> ').

To get the one-sided value for the superiority test (if applicable): re-run the above code with alpha=0.025 and PDIFF=controlu('<control> ').

If the model with the unstructured correlation matrix fails to converge then modifications shall be made in the following order.

1. Re-instate the GROUP = trtc option and replace un by VC
2. Re-instate the GROUP = trtc option and replace un by CS
3. Re-instate the GROUP = trtc option and replace un by AR(1)
4. Re-instate the GROUP = trtc option and replace un by TOEP
5. Remove the GROUP = trtc option and replace un by VC
6. Remove the GROUP = trtc option and replace un by CS
7. Remove the GROUP = trtc option and replace un by AR(1)
8. Remove the GROUP = trtc option and replace un by TOEP

Removing the GROUP = trtc option assumes that the correlation matrix is equal across the treatment arms. The other modifications replace the unstructured correlation matrix by those with the following assumptions (in the same order) variance components, compound symmetry, first order autoregressive and Toeplitz.

=====

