### 2.6.4 Supportive analyses

For supportive and sensitivity analyses of the primary analysis where p-values are presented, the one-sided non-inferiority p-value for the shifted hypothesis ( $\mu_{DI} - \mu_{PRN} \leq -\Delta$ ) will also be provided in addition to the p-value for the (unshifted) null hypothesis.

The primary analysis will be repeated for the PPS (LOCF) using the same methodology as outlined in [Section 2.6.2](#). Since this is a non-inferiority trial, the corresponding results obtained for the PPS are regarded as of almost equal importance for the interpretation. Any major discrepancies in the results across analyses will be investigated as necessary.

The same model as the one used for the primary analysis will be repeated for the FAS on observed data (as observed) as well as PPS (as observed). The primary efficacy variable D0 will be calculated as follows:

$$D0 = [(sum of non-missing BCVA1, BCVA2, \dots BCVA12 values) / k] - BCVA0$$

where k (k = 1, \dots, 12) is the number of non-missing BCVA values between month 1 and month 12, inclusively, and BCVA0, BCVA1, \dots BCVA12 are as defined in [Section 2.6.1](#).

Furthermore, the mean visit-averaged change from baseline in BCVA from month 1 to EoT, will be compared between the two treatments based on the assumption of a “Missing at Random (MAR)” process, i.e. assuming that the statistical behavior of a patient who drops out post-withdrawal is the same as that for a patient remaining in the study and sharing the same covariates and the same measurement history. This analysis will be based on a mixed model repeated measurement (MMRM). The MMRM model will be fit to all the BCVA data collected from month 1 to month 12 inclusive. The MMRM analysis will include subject as a random effect, and the following as effects:

Categorical variables

- treatment
- center

- visit

Continuous variables

- baseline BCVA

Interactions

- treatment by visit interaction
- visit by baseline BCVA interaction

A term for visit will be included in the repeated statement and an unstructured correlation matrix will be used thus allowing adjustment for correlations between time points within patients. A Kenward-Roger approximation will be used for the denominator degrees of freedom.

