If the model with the unstructured correlation matrix fails to converge then the following correlation structures should be fitted; variance components, compound symmetry, first order autoregressive and Toeplitz. The value of the Akaike Information Criteria (AIC) should be considered to choose the most appropriate model. Note that, other things being equal, the model with the smallest AIC is preferred. In case of inadequate results, further modification of the model may be required.

Additional sensitivity analyses of the primary analysis (using the same methodology as outlined in [Section 2.6](#)) for FAS (LOCF) will be performed:

- using all data from baseline to EoS (visit-averaged change from baseline in BCVA from month 1 to EoS).  
This analysis is meant to additionally include the data collected between EoT and EoS for those patients who prematurely discontinue from treatment but stay in the study.
- excluding patients who discontinue treatment early but stay in the study
- using all data for patients who reach month 12 (i.e. completers, patients who do not prematurely discontinue treatment or the study early)

The LS (“adjusted”) means for each treatment arm and estimates of the difference (DI - PRN) will be given along with the respective two-sided, 95% CI. P-values will be presented for the treatment difference.

The difference in treatment effects will be illustrated graphically using a forest plot for each analyzed population for the primary analysis and each sensitivity and supportive analysis: the estimates of differences in visit-averaged change from baseline in BCVA from month 1 to the timepoint of interest, between the two treatment arms will be presented along with respective two-sided 95% CIs.

Furthermore, a frequency table presenting the number and percentage of patients based on FAS (LOCF) with a change of 5, 10, or 15 letters in BCVA from baseline at Month 12 will be provided.

KM curves and descriptive statistics will be provided for time to:

- first gain in BCVA from baseline of  $\geq 10$  letters
- first gain BCVA from baseline of  $\geq 15$  letters

for the FAS. The main focus of this study is to understand the effect of the two treatments of interest. Therefore, time to first gain  $\geq x$  letters (where  $x=10$  or  $15$  letters) will be derived for:

1. up to EoT

This means:

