## 3 Sample size calculation

A sample size of 133 patients per treatment arm will have 90% power to establish non-inferiority at a margin of 4 letters for the 0.5 mg ranibizumab “at investigators discretion” dosing regimens in comparison to 0.5 mg ranibizumab PRN in the mean average change in BCVA based on a one-sided 0.025 significance level, assuming a treatment difference of 0 letters, a SD of 10 letters and an underlying normal distribution for an unstratified t-Test (nQuery Advisor 7.0).

The Phase III study (RESTORE) results in the FAS suggest a mean average change in BCVA of 6 letters with a SD of about 7-8 letters for ranibizumab. To account for some more variability related to the re-treatment concepts and subgroup treated with additional PRP laser in this study as compared to RESTORE, a SD of 10 letters is assumed. To account for some drop outs 150 patients will be randomized per treatment arm.

As outlined in the study protocol, section “Summary of protocol amendments” (study protocol version no.1 including Amendment 1); further recruitment of patients into this study was revised and reduced. New and relevant scientific evidence regarding treatment patterns with ranibizumab was published which did not justify continuing the trial with newly included

patients. Therefore recruitment was terminated at the time when 135 patients were enrolled into the study, resulting in a reduced sample size present for analysis.

As a consequence results are to be interpreted in a purely descriptive manner. With an estimate of about 120-150 patients to be enrolled by end of recruitment the expected power would be about 55-60% and will be evaluated accordingly.

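### SAP 5.2.1 and 2.6.4 give conflicting rules for an unstructured MMRM that fails to converge; read literally, 5.2.1 stops at a model that treats one patient's visits as independent

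*SAP*

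**What the plan says.** SAP 2.6.4 describes a supportive analysis under a missing-at-random assumption: an MMRM of BCVA from month 1 to month 12 with an unstructured within-patient matrix. It states that "The MMRM analysis will include subject as a random effect". If the unstructured fit does not converge, variance components, compound symmetry, AR(1) and Toeplitz are to be fitted. Then "The value of the Akaike Information Criteria (AIC) should be considered to choose the most appropriate model", with the smallest value preferred.

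The code part of SAP 5.2.1 handles the same event differently: "If the model with the unstructured correlation matrix fails to converge then modifications shall be made in the following order". Step 1 of its eight steps reads "Re-instate the GROUP = trtc option and replace un by VC". Steps 2 to 4 replace VC by CS, AR(1) and TOEP. Steps 5 to 8 repeat the four structures without the GROUP option. AIC is not mentioned there. The printed PROC MIXED call has a REPEATED statement with the chosen covariance type and no RANDOM statement.

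Under SAP 2.6.4 the supportive analyses that show p-values also carry the one-sided non-inferiority p-value, and each is drawn in the forest plot.

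**The concern.** TYPE=VC in a REPEATED statement, with no random subject effect, is a diagonal within-patient matrix. Twelve readings on one eye then count as twelve independent pieces of information. The Kenward-Roger correction does not repair this, because it works within the assumed covariance structure. With positive within-patient correlation, the standard error of the visit-averaged treatment contrast is too small and the error favours a finding of non-inferiority.

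The order matters because non-convergence is the only trigger. The diagonal model practically always converges, so a programmer who follows 5.2.1 to the letter never reaches CS, AR(1) or TOEP. A falsely narrow interval could then sit beside the ANCOVA results in the forest plot and look like strong support.

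**Working it through.** **Inputs from the documents.** SAP 3 gives a "one-sided 0.025 significance level", a margin of 4 letters and, for the visit-averaged change, "assuming a treatment difference of 0 letters, a SD of 10 letters and an underlying normal distribution for an unstratified t-Test". SAP 1.1 gives 135 patients randomized 1:1. SAP 2.6.4 gives up to 12 post-baseline readings. Protocol 5.5.3.3.1 lets DI visits lie up to 3 months apart after the initial phase.

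**Assumption.** The within-patient correlation ρ is in neither document, so a range is shown.

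**Step 1: the plan's own figure.** SAP 3 says: "A sample size of 133 patients per treatment arm will have 90% power to establish non-inferiority at a margin of 4 letters". By the normal approximation, n = 2 × 10² × (1.960 + 1.282)² / 4², about 131.4, so 132 per arm. With the noncentral t the power is 0.899 at 132 and 0.901 at 133. The stated 133 is reproduced.

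**Step 2: the correct interval at 135 patients.** SE = 10 × √(2/67.5) = 1.72 letters, and 1.96 × 1.72 = 3.37. The correct 95% half-width is about 3.4 letters.

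**Step 3: the VC interval with equal correlation and m = 12.** The variance of a patient's average is σ²[1 + (m − 1)ρ]/m. VC uses σ²/m. The width ratio is therefore r = 1/√(1 + 11ρ). Coverage is 2Φ(1.96r) − 1, and the one-sided error at a true difference of −4 is 1 − Φ(1.96r).

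| ρ (assumed) | 1 + 11ρ | r | VC half-width (letters) | Coverage | One-sided error |
|---|---|---|---|---|---|
| 0.1 | 2.1 | 0.69 | 2.3 | 82% | 8.8% |
| 0.2 | 3.2 | 0.56 | 1.9 | 73% | 13.7% |
| 0.3 | 4.3 | 0.48 | 1.6 | 66% | 17.2% |
| 0.5 | 6.5 | 0.39 | 1.3 | 56% | 22.1% |
| 0.7 | 8.7 | 0.34 | 1.1 | 49% | 25.3% |
| 0.8 | 9.8 | 0.32 | 1.1 | 47% | 26.6% |

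The ratio falls below one half only when 1 + 11ρ > 4, that is, ρ > 3/11 = 0.27.

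**Step 4: settings where the narrowing is smaller.**
- AR(1), 12 readings, r = √(m / sum of all entries of the correlation matrix): 0.61 at lag-1 correlation 0.5, 0.54 at 0.6, 0.48 at 0.7, 0.41 at 0.8.
- PRN with 12 readings and DI with 6 (assumed). The effective m is 2/(1/12 + 1/6) = 8, so r = 1/√(1 + 7ρ): 0.57 at ρ = 0.3, 0.51 at 0.4, 0.47 at 0.5, 0.41 at 0.7.

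**Step 5: simulation with the SAP's mean model.** This used 135 patients, 30 centers, visit, treatment by visit and baseline by visit, one common variance and no GROUP option. There were 20 to 25 trials per setting, so only the width ratios are used.
- All 12 visits: ratios 0.68, 0.47, 0.37 and 0.31 at ρ = 0.1, 0.3, 0.5 and 0.7.
- DI monthly to month 4, then gaps of 1 to 3 months: 0.74, 0.52, 0.42 and 0.36.
- AIC preferred VC to CS in 0 of 180 trials. CS was evaluated at the true ρ; estimating ρ could only raise its likelihood.

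**Step 6: the two rules side by side.** Under 2.6.4, AIC would in practice reject VC. VC residuals plus a random subject intercept imply compound symmetry, which also restores the correlation. Under 5.2.1 as printed, neither safeguard is present.

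**The case against.** The strongest reply is that the SAP body already covers this. Section 2.6.4 names the AIC rule and the random subject effect, and either one removes the problem. It also allows further modification if results are inadequate. The 5.2.1 list can be read as the order in which to fit the same four structures. Its code is labelled illustrative and has loose ends: it speaks of re-instating a GROUP option that is already there, and it refers to a slice option that is absent. This stands in part. It shows that the intended analysis is probably sound. It does not settle which section governs, because 5.2.1 is worded as a mandatory sequence.

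A reader might infer three stronger things that the documents do not support.
- **That the interval is necessarily less than half the correct width.** This needs ρ above 0.27 with 12 readings, above about 0.4 if DI averages 6, or an AR(1) lag-1 correlation near 0.7. Repeated BCVA readings may well reach such values, but no figure is given.
- **That this is the only check without LOCF.** SAP 2.6.4 also repeats the ANCOVA on observed data for the FAS and the PPS. SAP Table 5-3 even lists the MMRM on FAS (LOCF), while 2.6.4 speaks of collected data. With LOCF, DI sparsity would matter less and the correlation would be higher.
- **That the fallback will probably be needed.** The unstructured matrix has 12 × 13/2 = 78 parameters per arm, for about 67 patients, so failure is plausible. No convergence rate has been shown.

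**Conclusion.** The two sections conflict, and 5.2.1 is wrong as written: its first fallback drops within-patient correlation, and a literal reading stops there. The direction is anti-conservative for any positive correlation. With 12 readings and equal correlation, even ρ = 0.1 more than triples the nominal one-sided error (8.8% against 2.5%). The exact size rests on an assumed ρ and is smaller with sparse DI visits or AR(1) correlation. It also requires that the unstructured fit fails, that 5.2.1 is followed over the AIC rule, and that no random subject effect is added.

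The reach is limited. The primary ANCOVA uses one averaged value per patient and is untouched, and SAP 1.1 makes all analyses exploratory. The point merits correction because the affected result carries a non-inferiority p-value and appears in the forest plot. It does not put the primary result in doubt.

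**What to change.** In SAP 5.2.1:
- Delete steps 1 and 5, or allow VC only together with a RANDOM subject intercept.
- If the unstructured fit fails, fit CS, AR(1) and TOEP, each with and without GROUP, and take the smallest AIC.

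In SAP 2.6.4, state the same rule and the same list of structures. Say there which structure the random subject effect belongs to, because it is redundant next to an unstructured or compound-symmetry matrix. Make the printed code match.

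The cost is a few lines of SAP text and code, and a wider supportive interval than VC would give.

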### **SAS code for backward stepwise regression analysis**

For the appropriate treatment difference, the treatment arms should be sorted or coded appropriately before using this model.

The analysis will be performed using SAS procedure PROC GLMSELECT as below. Note that for this illustrative example:

- the data are stored in the file data\_set
- treatmentvar = treatment variable
- responsevar = dependent variable
- stratavar = stratification variable
- bsl = baseline value of the responsevar
- alpha = significance level (i.e. 0.05 produces two-sided 95% CI)
- n = the first **n** effects listed in the MODEL statement which are forced to be included in all models

```
PROC GLMSELECT DATA = <data_set>;
CLASS <stratavar> <treatmentvar>;
MODEL <responsevar> = <stratavar> <treatmentvar> <bsl> / DETAILS = all SELECTION =
backward INCLUDE = <n>;
LSMEANS <treatmentvar> / PDIFF = all CL alpha = <alpha> OM;
RUN;
```

=====

### SAS code for Wilcoxon rank sum test

Wilcoxon Rank Sum Test will be presented as a nonparametric comparison additionally to the primary analyses.

For the appropriate treatment difference, the treatment arms should be sorted or coded appropriately before using this model.

Wilcoxon Rank Sum Test will be presented as a non-parametric comparison additionally to the primary analyses.

- the data are stored in the file data\_set
- treatmentvar = treatment variable
- responsevar = dependent variable
- alpha = significance level

```
PROC NPAR1WAY DATA = <data_set> HL alpha = <alpha>;
CLASS <treatmentvar>;
VAR <responsevar>;
RUN;
```

=====

### SAS Codes for Kaplan-Meier Plot

The time to event analysis will be performed using the SAS procedure PROC LIFETEST.

Note that for this illustrative example:

- the data are stored in the file data\_set
- timevar = survival time
- censorvar = censoring variable (Note: 1 indicates a censored time)
- stratavar = stratification variable

```
ODS GRAPHICS ON;  
PROC LIFETEST DATA=<data_set> PLOTS=survival (failure test at  
risk(outside(0.15))=0 to 360 by 30);  
TIME <timevar> * <censorvar> (1);  
STRATA <stratavar>;  
RUN;
```

The option OUTSIDE(0.15) reserves 15% of the vertical graph window for the at-risk table. It can be adjusted.

=====

### SAS Codes for Kaplan-Meier Table

The summary statistics for time to event analysis will be performed using SAS procedure PROC LIFETEST.

Note that for this illustrative example:

- the data are stored in the file data\_set
- timevar = survival time
- censorvar = censoring variable (Note: 1 indicates a censored time)
- stratavar = stratification variable

```
PROC LIFETEST DATA = <data_set>;  
TIME <timevar> * <censorvar> (1);  
STRATA <stratavar>;  
ODS OUTPUT CensoredSummary=censorsum  
      Means=mean  
      Quartiles=quartiles;  
RUN;
```

=====

### SAS Codes for Pearson's and Spearman's correlation coefficient

Pearson's and Spearman's correlation coefficient will be obtained using SAS procedure PROC CORR.

Note that for this illustrative example:

- the data are stored in the file data\_set
- var1 = variable 1 to obtain the correlation of variable 1 and variable 2
- var2 = variable 2 to obtain the correlation of variable 1 and variable 2

```
PROC CORR DATA = <data_set> PEARSON SPEARMAN;  
VAR <var1> <var2>;  
RUN;
```

### 5.3 Rule of exclusion criteria of analysis sets

**Table 5-4 Protocol deviations that cause subjects to be excluded**

Deviation ID	Description of Deviation	Exclusion from Analyses
I00	Not signed Informed Consent	Excluded from all analysis
I01	Subject is less than 18 years of age or age missing.	Not reportable
I02aa	Patients with diabetes but type of diabetes is not known.	Not reportable
I02ab	Patient with no History of diabetes.	Excluded from PP analysis
I02b	Glycosylated hemoglobin greater than 12 percent, i.e. 107 mmol per mol Hb, at screening Visit 1	Reportable
I03a	Patients without visual impairment due to DME in the study eye	Excluded from PP analysis
I03b	Patients without visual impairment due to DME in the fellow eye	Not reportable
I04a	BCVA less than 24 in the study eye, using ETDRS-like visual acuity testing charts at a testing distance of 4 resp. 1 meters (approximate Snellen equivalent of 20/32 to 20/320) at screening or baseline	Not reportable
I04b	BCVA greater than 78 in the study eye, using ETDRS-like visual acuity testing charts at a testing distance of 4 resp. 1 meters (approximate Snellen equivalent of 20/32 to 20/320) at screening or baseline	Excluded from PP analysis
I05	Concomitant conditions in the study eye, which prevent improvement of visual acuity on study treatment	Excluded from PP analysis (medical review)
E01aa	Active intraocular inflammation grade trace or above in the study eye at enrollment.	Excluded from PP analysis (medical review)
E01ab	Active intraocular inflammation grade trace or above in the fellow eye at enrollment.	Not reportable
E01a	Women who are pregnant or breast feeding.	Not reportable
E02	Any active infection in either eye at the time of enrollment e.g. conjunctivitis, keratitis, scleritis, endophthalmitis.	Reportable (medical review)
E03	History of uveitis in either eye at any time.	Not reportable
E04	Structural damage within 0.5 disc diameter of the center of the macula in the study eye likely to preclude improvement in VA, incl. atrophy of RPE, subretinal fibrosis, laser scar(s).	Excluded from PP analysis (medical review)
E05	Patients with both, a BCVA score of greater than 73 letters and a central subfield thickness of less than 300 micro meter in the study eye.	Excluded from PP analysis (medical review)
E06	Uncontrolled glaucoma in either eye at screening. IOP greater than 24 mmHg on medication or according to investigator judgment.	Excluded from PP analysis (medical review)
E07	Neovascularization of the iris in either eye.	Not reportable
E08	Vitreous hemorrhage impairing the adequate diagnosis of DME in the	Excluded from

Deviation ID	Description of Deviation	Exclusion from Analyses
	study eye.	PP analysis
E09	Clinically relevant vitreofoveal adhesion, vitreofoveal traction or epiretinal membrane with foveal involvement likely to prevent improvement of BCVA, according to investigator opinion.	Not reportable
E10	Proliferative vitreoretinopathy in study eye.	Not reportable
E11	History of retinal detachment, retinal tear or macular hole in the study eye.	Not reportable
E12	Neovascularization covering an area greater than or equal to 2 disc areas within the macula defined as area with 6mm diameter centered on the fovea for study eye.	Not reportable
E13	Patients who are monocular or have a BCVA score in the non-study eye less than 24 letters approximate Snellen equivalent of 20 per 320 at Visit 1.	Not reportable
E14	Any intraocular surgery in the study eye within 4 months prior to randomization.	Reportable (medical review)
E15a	Vitrectomy/vitreoretinal surgery - In the medical history or planned for study eye.	Reportable (medical review)
E15b	Planned vitrectomy or vitrectomy in last 3 months in fellow eye.	Not reportable
E16	Planned medical or surgical intervention during the 12 months study period likely to interfere with study schedule or outcomes.	Reportable (medical review)
E17	Panretinal or focal or grid laser photocoagulation in study eye within 3 months prior to randomization unless sufficient documentation of laser photocoagulation in that period of time is available.	Reportable (medical review)
E18a	Treatment with anti-angiogenic drugs within 1 month for fellow eye prior randomization.	Not reportable
E18b*	Treatment with anti-angiogenic drugs within 3 months (84 days) for study eye prior randomization.	Excluded from PP analysis
E19	Use of other investigational drugs at the time of enrollment, or within 3 months or 5 half-lives from enrollment, whichever is longer.	Reportable (medical review)
E20	History of intravitreal corticosteroid treatment in phakic study eye.	Reportable (medical review)
E21	Intravitreal corticosteroids in post-cataract surgery study eye (aphakic or pseudophakic, without damaged posterior capsule) within 3 months or 6 months for dexamethasone implant (Ozurdex®) or 3 years for fluocinolone implant (Iluvien®) prior to randomization.	Excluded from PP analysis
E22	Ocular conditions in the study eye that require chronic concomitant therapy with topical ocular corticosteroids.	Reportable (medical review)
E23	Stroke less than 4 months prior to screening.	Not reportable
E24	Renal failure requiring dialysis or renal transplant.	Not reportable
E25	Untreated diabetes mellitus.	Not reportable
E26	BP defined as systolic value of greater than 160 mm Hg or diastolic value greater than 100 mm Hg at screening or randomization.	Not reportable
E27	Conditions that require chronic concomitant therapy with systemically administered corticosteroids.	Reportable (medical review)
E28	Current use of Medications known to be toxic to the lens, retina or	Reportable

Deviation ID	Description of Deviation	Exclusion from Analyses
	optic nerve, including Deferoxamine, Chloroquine or hydroxychloroquine, Plaquenil, Tamoxifen, Phenothiazines and Ethambutol.	(medical review)
E29	Use of any systemic anti VEGF drugs within 3 months prior to Screening.e.g. bevacizumab, ziv afibbercept.	Excluded from PP analysis
E30	Known hypersensitivity to fluorescein or ranibizumab or any component thereof or drugs of similar chemical classes.	Not reportable
E31	Disease severity/medical condition/ treatment expected to progress, recur, or change to an extent may bias the assessment of clinical status of patient or special risk to a significant degree.	Reportable (medical review)
D01	MH or AE - Rhegmatogenous retinal detachment or Stage 3 or 4 macular hole in the study eye and no treatment discontinuation.	Excluded from PP analysis (medical review)
D02	MH or AE - Transient ischemic attack or a stroke during the study and no treatment discontinuation	Not reportable
D03	Pregnancy but patient not discontinued from trial.	Excluded from PP analysis
D04	Vitrectomy that did not lead to discontinuation of study treatment.	Excluded from PP analysis
S01	Patient received Ranibizumab from another study or as commercially available Lucentis	Not reportable
S02	Study task injection of ranibizumab was performed by untrained site personnel.	Not reportable
S03	Patient received study medication which was outside the allowed temperature range and should have not been used any more according to guidelines or QP decision.	Reportable (medical review)
M01	Concurrent use of any anti-VEGF agents either systemic or in the study eye (only permitted in the fellow eye).	Excluded from PP analysis
M02	Concurrent use of peribulbar or intraocular corticosteroids in study eye.	Excluded from PP analysis
M03	Concurrent use of intraocular corticosteroids inserts in study eye.	Excluded from PP analysis
M04	Systemic medications known to be toxic to the lens, retina or optic nerve, including Deferoxamine, Chloroquine or hydroxychloroquine, Tamoxifen, Phenothiazines and Ethambutol.	Reportable (medical review)
M05	Treatment with glitazones or fingolimod when newly started during the study.	Reportable (medical review)
M06	Other investigational drugs and interventions of any type.	Excluded from PP analysis
O02	Missing FLA assessment at visit 1 for both eyes.	Not reportable
O03	Missing FLA assessment at visit 14 for both eyes.	Not reportable
O04a	Missing FP assessment at visit 1 for both eyes.	Not reportable
O04b	Missing FP assessment at EOS visit for both eyes.	Not reportable

Deviation ID	Description of Deviation	Exclusion from Analyses
O05	Missing BCVA in study eye at any visit.	Not reportable
O06	Missing BCVA in fellow eye at any Screening, EOS and EOT visits.	Not reportable
O07	Missing OCT assessment in study eye at any visit.	Not reportable
O08	Missing OCT assessment in fellow eye at Screening, EOS and EOT visits.	Not reportable
O09a	Intraocular Pressure was not measured prior treatment for study eye.	Not reportable
O09b	Intraocular Pressure was not measured after treatment for study eye.	Not reportable
O10	Inadequate training of Investigators during study conduct.	Not reportable
O12	Screening not 28 to 3 days before Baseline.	Not reportable
O14	End of Study Visit not after last treatment of study medication.	Not reportable
O15	Focal or grid laser photocoagulation done prior 3 months after baseline.	Reportable (medical review)
O16	Any Treatment cycle (PRP) was not completed within 6 weeks	Reportable (medical review)
O17	Panretinal Photocoagulation at baseline or at least within 3 months after randomization in both arms for study eye for respective patients	Reportable (medical review)
O19	PDR laser spots smaller than 500 micro meter for respective patients	Not reportable
O20	Less than 12 weeks between PRP-treatments for respective patients	Not reportable
O21	VA examination done by non-certified personnel for both eyes or study eye only.	Not reportable
O22	OCT examination done by personnel not certified for study.	Not reportable
O23	OCT examination done with a device not registered for study.	Not reportable
O25	FP examination done with a device not registered for study.	Not reportable
O28	BCVA examination done in a non-certified room.	Not reportable
O31	General GCP or CSP compliance issue.	Not reportable
O32	VA assessor did not change from Visit 1 to Visit 4 (same at any 2 consecutive visits up to V4).	Not reportable
O33	VA assessor did not change from Visit 5 onwards (same at any 2 consecutive visits from V5 onwards).	Reportable
O35**	BCVA measurement was performed 2 days later then visit 1. V1 was split in 2 days.	Not reportable
O37	Same BCVA-Assessor at consecutive months visit 5 onwards.	Reportable
O39	BCVA assessor, who performed other study tasks and was subsequently unmasked to treatment arm, was still active as BCVA assessor.	Reportable

Deviation ID	Description of Deviation	Exclusion from Analyses
O40	Minimum PRP treatment of 1200 burns for study eye was not given for respective patients.	Reportable (medical review)
O41	Subjects who had completed trial and have number of days difference between V2 to V14 (EOS) is above 393 days.	Excluded from PP analysis
O42	Minimal Injection window period must be 28 days.	Not reportable

\* In PD E18b the 3 months criterion was clarified to be 84 days (which is based on 7 days by 4 weeks by 3 months)

\*\* PD O34 was retired as a PD and will only be handled as an edit check by data management in the database

